method combining mechanical and chemical debridement with 1.7% HP gel . The HP gel is directed into periodontal pockets via a custom tray, as an aid to manage biofilms better for patients with gingivitis and periodontitis. The FDA approved  $\leq 3\%$  HP gel as an oral debriding agent and an oral wound cleanser. The FDA also cleared the prescription tray branded as the Perio Tray® (Perio Protect, St. Louis, MO) as a subgingival delivery medical device in 2004 (21 C.F.R. § 872.6870). Customized extensions of the tray support the customized seal to direct the gel deep down into the sulcus or periodontal pocket and overcome the crevicular fluid flow .

Custom tray application of the HP gel as an adjunct to SRP in the treatment of chronic periodontitis has been investigated. In randomized controlled studies, it was demonstrated that significant reduction of probing depth (PD) and bleeding without mechanical intervention were seen after two weeks of HP prescription tray regimen followed by SRP and the results were maintained for up to six months with the daily use of HP prescription trays for 10 weeks . The prescription tray delivery of HP gel as an adjunctive to SRP was effective before and after full-mouth SRP in reducing PD about 1mm over SRP alone for six months in chronic periodontitis patients . However, there is currently no randomized control clinical study evaluating the differences in the duration effects of the treatment in chronic periodontitis patients with customized delivery of hydrogen peroxide gel.

The primary objectives of this randomized, controlled, single-blind, parallel clinical study are: (1) to examine if the prescription tray delivery of HP gel adjunctive to SRP results in a greater clinical improvement than SRP alone over a six-month period; and (2) to

evaluate whether the custom tray delivery of the HP gel can decrease inflammation prior to SRP.

The secondary objective is to compare if there is a difference between the length of treatment of adjunctive HP gel (3-months versus 6-months). It is hypothesized that adjunctive HP therapy will provide additional clinical benefits in PD reduction, attachment gain, and reduction of bleeding on probing (BOP) compared to SRP alone.

Null Hypotheses:

There is no significant difference between the treatment groups (SRP + HP13 vs. SRP + HP26 vs. SRP alone) with regards to reduction in PD.

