#### **Screening and Recruitment of Participants**

A study population of sixty qualifying adults was selected by screening from patients who were referred to the Graduate Periodontics Clinic at Loma Linda University School of Dentistry. All patients received a comprehensive periodontal examination and those diagnosed generalized moderate to severe chronic periodontitis  showing minimum of one site with PD of  $\geq 5$  mm and bleeding on probing (BOP) in at least two quadrants was considered for subject recruitment. Patients who met the inclusion and exclusion criteria were eligible to participate in the study (see Eligibility and Exclusion criteria) and the patients were asked if they were willing to be a subject. Verbal and written informed consent were given to the subject outlining the purpose, timeline, as well as potential risks and benefits of participation. Once the patient accepted and was recruited as a subject they were randomized into groups by a predetermined random group assigner (see Randomization: Sequence, Allocation, and Implementation).

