## **Exclusion Criteria**

- 1) Any systemic conditions or medication intake that can alter periodontal status (e.g. uncontrolled diabetes (with <3-month recent HbA1c of  $>8.5\%$ ), anti-seizure medication, immunosuppressant, and calcium channel blockers with clinical sign of gingival overgrowth.
- 2) Immune-compromised state.

- 3) Any current heavy smoking habits (>10 cigarettes/day)
- 4) Any medical condition or history requiring prophylactic antibiotic coverage prior to dental treatment.
- 5) Females who are lactating or pregnant (as determined by medical history) or planning to become pregnant for the duration of the study.
- 7) Physical limitations/restrictions compromising oral hygiene procedures.
- 8) The presence of significant oral soft tissue pathology and/or lesions associated with ill-fitting appliances or restorations.
- 9) Tooth mobility associated with advanced periodontal disease (e.g. score of >2 using Miller Classification).
- 10) Any temporomandibular joint disorders.
- 11) Grossly carious, orthodontically banded, and third molars will not be included in the tooth count.
- 12) Presence of any significantly tipped, crowded, or largely defective restorations.
- 13) Any extreme adverse events relating to the use of HP gel (e.g. prolonged tooth hypersensitivity or aberrant soft tissue/mucosal reaction)

All participants were screened and evaluated at Loma Linda University School of Dentistry Graduate Periodontics Department. There are three groups of 20 patients, two therapy test groups and the control group.

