### **Treatment Phase**

The treatment phase began with non-surgical periodontal treatment. The two therapy test groups will have used their customized application HP gel for four weeks prior to the start of treatment. Non-surgical periodontal treatment consisted of 1-, or 2-visit SRP using ultrasonic and hand instrumentation with local anesthesia. Surfaces were to be deemed clean and debrided when subgingival deposits cannot be tactiley detected and the root surface feels smooth to the operator. Re-evaluation of SRP was done 8 weeks after the last session of SRP, at week 13. One therapy test group stopped using the HP

therapy at the re-evaluation visit (HP13). Whereas the other test therapy group received impressions for a new customized tray to continue application of HP therapy for an additional 13 weeks (HP26) to the termination of the study.

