### **Custom HP Tray Application**

The principal investigator supervised first use of trays and HP gel and, if needed, adjustment were made to trays so that it seated completely and comfortably in the subject's mouth while maintaining an adequate seal. Each subject applied a thin ribbon of gel throughout tooth indentations to provide a dosage of ~0.75 gram in each tray using a mass scale. Treatment frequency will be fixed throughout the study duration: Start of Treatment (Visit 2, Week 0) to 8-weeks following SRP (Visit 5, Week 13): two treatments per day, 15 minutes each

Subjects in the treatment groups documented tooth brushing and the gel tray applications in calendar journals for the entire duration of the study. Subject compliance was estimated throughout the study by reviewing diaries and by massing gel tubes at each visit. Patients were instructed to bring in their treatment tubes to each visit.

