## **Statistical Analysis**

The primary outcome variables are PD reduction, RAL gain, and reduction in BOP. PD data was computed to provide a mean score per mouth. Secondary efficacy variables were BOP, and MQH. BOP was computed to provide a mean score per mouth for each clinical assessment and were analyzed using repeated measures (ANOVA). Outcome variable data analysis consisted of between-treatment and within-treatment (longitudinal) comparisons of PD and CAL at all examination time points using parametric procedures. Between-treatment and within-treatment comparisons employed baseline data and analysis of covariance (ANCOVA) for follow-up data. All comparisons were performed using two-sided hypothesis tests, and employed a 0.05 level of significance.

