Figures 4, 5, 6, and 7 show baseline, 4-week, re-evaluation, and final MQH plaque scores. Plaque scores varied throughout the four timepoints with no obvious differences between groups.

[figure not shown]

Figure 5. Baseline MQH scores for A) SRP, B) HP13, and C) HP26

[figure not shown]

Figure 6. 4-Week MQH scores for A) SRP, B) HP13, and C) HP26.

[figure not shown]

Figure 7. Re-Evaluation MQH scores for A) SRP, B) HP13, and C) HP26.

[figure not shown]

Figure 8. Final MQH scores for A) SRP, B) HP13, and C) HP26.

[figure not shown]

Figure 9. Mean BOP in each group, SRP, HP13, and HP26

[figure not shown]

Figure 10. BOP % in pockets initially <5 mm

[figure not shown]

Figure 11. BOP % in pockets initially  $\geq 5$ mm

Figure 8 shows mean BOP. Baseline mean BOP was 45% for SRP, 57% for HP13, and 63.1% for HP26. At 4-weeks, mean BOP was 45% for SRP, 60% for HP13, and 44% for HP26. At re-evaluation, mean BOP was 37% for SRP, 30% for HP13, and 27% for HP26. Final mean BOP scores were 44% for SRP, 33% for HP13, and 28% for HP13. Mean BOP was significantly reduced in all groups between 4-week examination and re-evaluation with mean BOP scores at final examination staying similar to levels at re-evaluation for HP13 and HP26 groups. Mean BOP scores at final examination group for SRP group was similar to baseline.

Figure 9 shows BOP % in pockets initially  $< 5$ mm. At baseline, 24% of pockets  $< 5$ mm were BOP for SRP, 47% for HP13, and 52% for HP26. At 4-week examination BOP % were 29% for SRP, 44% for HP13, and 35% for HP26. At re-evaluation, BOP %

was 27% for SRP, 21% for HP13, and 22% for HP26. At the final exam, BOP % was 33% for SRP, 26% for HP13, and 22% for HP26.

Figure 10 shows BOP % in pockets initially  $\geq 5$ mm. At baseline, BOP % was 92% for SRP, 81% for HP13, and 91% for HP26. At 4-week examination, BOP % was 91% for SRP, 93% for HP13, and 83% for HP26. Re-evaluation BOP % was 91% for SRP, 78% for HP13, and 75% for HP26. At final examination, BOP % was 88% for SRP, 79% for HP13, and 78% for HP26.

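### Primary objective 2 asks gel versus no gel at week 4, when HP13 and HP26 have the same assigned treatment, but no combined-gel contrast against SRP is specified or reported

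*Combined protocol and SAP*

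**What the plan says.** **The question.** The second primary objective in the Introduction is to "evaluate whether the custom tray delivery of the HP gel can decrease inflammation prior to SRP". Length of gel use (3 versus 6 months) is a separate, secondary objective. The null hypotheses that follow set HP13, HP26 and SRP alone side by side as three groups, without naming a time point.

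**The treatment.** Under Treatment Phase, "The two therapy test groups will have used their customized application HP gel for four weeks prior to the start of treatment". Custom HP Tray Application gives one frequency for both gel arms: "Start of Treatment (Visit 2, Week 0) to 8-weeks following SRP (Visit 5, Week 13): two treatments per day, 15 minutes each". In the Study Schedule the gel arms share one list of visits. They part at the week-13 visit, where HP13 stops gel and HP26 has impressions taken for a new tray. The week-13 measurements belong to that same visit.

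**The analysis.** Statistical Analysis states: "Outcome variable data analysis consisted of between-treatment and within-treatment (longitudinal) comparisons of PD and CAL at all examination time points using parametric procedures". It adds ANCOVA for follow-up data and repeated-measures ANOVA for BOP, and "All comparisons were performed using two-sided hypothesis tests, and employed a 0.05 level of significance". No contrast among the three arms is given.

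**The report.** Results are printed arm by arm at every visit, for example "At 4-weeks, mean BOP was 45% for SRP, 60% for HP13, and 44% for HP26". No combined-gel figure appears.

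**The concern.** At week 4 nothing in the assigned treatment separates HP13 from HP26, so the comparison that matches objective 2 is all gel patients against SRP. The plan does not name it.

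Two things are at stake. First, if objective 2 is answered by a three-group test or by one gel arm at a time, precision that the design already provides is lost. Second, the reader is left with two separate answers about the same treatment, and on the printed week-4 figures they point in opposite directions relative to SRP.

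**Working it through.** **Planned allocation.** The input is "There are three groups of 20 patients, two therapy test groups and the control group". The documents give no power, effect size, SD or dropout rate, so there is no derivation of the 60 to reproduce. Effects below are in units of the between-patient, baseline-adjusted SD. The values 0.6 and 0.8 are assumptions.

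Variance of a difference, in SD² units, is 1/n₁ + 1/n₂:
- One gel arm versus SRP: 1/20 + 1/20 = 0.100, SE = 0.316 SD.
- Combined gel versus SRP: 1/40 + 1/20 = 0.075, SE = 0.274 SD.
- Ratios: 0.075/0.100 = 0.75, so 25% less variance; √0.75 = 0.866, so a 13% smaller SE.

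Power at two-sided 0.05 uses the noncentral t with 57 df (noncentrality = effect/SE). The three-group test uses the noncentral F on 2 and 57 df with group means 0, d, d.

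| Assumed effect d | Combined gel vs SRP | Three-group F | One gel arm vs SRP |
|---|---|---|---|
| 0.8 SD | 82% | 72% | 70% |
| 0.6 SD | 58% | 47% | 46% |

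The contrast (HP13 + HP26)/2 versus SRP within a three-group model has variance 1/20 + ¼(1/20 + 1/20) = 0.075. With equal arms it is as precise as pooling.

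**Reported completers.** The Results give 3 SRP, 3 HP13 and 9 HP26:
- HP13 versus SRP: √(1/3 + 1/3) = 0.816 SD.
- HP26 versus SRP: √(1/3 + 1/9) = 0.667 SD.
- Combined gel (12) versus SRP: √(1/3 + 1/12) = 0.645 SD.
- Reduction in SE: 1 − 0.645/0.667 = 3% against HP26 versus SRP, and 1 − 0.645/0.816 = 21% against HP13 versus SRP.
- Equal-weight contrast: √(1/3 + ¼(1/3 + 1/9)) = 0.667 SD, no better than HP26 versus SRP. With unequal arms the weights matter.

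On 12 df at 0.8 SD, power is 20.8% combined against 19.8% for HP26 versus SRP. At 0.6 SD it is 13.7% against 13.2%.

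**Printed week-4 changes from baseline** (week 4 minus baseline, from the Results):

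| Outcome | HP13 | HP26 | SRP | HP13 − HP26 | HP13 − SRP | HP26 − SRP |
|---|---|---|---|---|---|---|
| PD, mm | 4.06 − 4.11 = −0.05 | 3.55 − 3.83 = −0.28 | 3.67 − 3.88 = −0.21 | 0.23 | 0.16 | −0.07 |
| RAL, mm | 7.29 − 6.97 = +0.32 | 6.69 − 7.04 = −0.35 | 7.02 − 7.16 = −0.14 | 0.67 | 0.46 | −0.21 |
| BOP, points | 60 − 57 = +3 | 44 − 63.1 = −19.1 | 45 − 45 = 0 | 22.1 | 3 | −19.1 |

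On all three outcomes SRP lies between the two gel arms, so the gel arms differ more from each other than either does from SRP.

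Combined gel minus SRP, with weights 3:9 taken from the six-month completers:
- PD: (3 × −0.05 + 9 × −0.28)/12 − (−0.21) = −0.01 mm.
- RAL: (3 × 0.32 + 9 × −0.35)/12 − (−0.14) = −0.04 mm.
- BOP: (3 × 3 + 9 × −19.1)/12 − 0 = −13.6 points.

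Week-4 numbers per arm are not given, so these weights are an assumption. Equal weights give BOP (3 − 19.1)/2 = −8.1 points, PD −0.165 + 0.21 = +0.05 mm and RAL −0.015 + 0.14 = +0.13 mm.

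**The case against.** **The plan prescribes no pairwise or omnibus test at week 4.** This stands. The analysis sentence speaks only of comparisons between treatments. The three groups come from the null hypotheses and the Results. The fault is an absent contrast.

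**Three groups are not wasteful in themselves.** This also stands. A three-group ANCOVA with the right contrast loses nothing at equal arms. The power loss above arises only if the omnibus test or a single pairwise test is used to answer objective 2.

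**The gain is negligible in the trial as completed.** This stands for HP26 versus SRP: three SRP patients set the limit.

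**No chance difference was presented as a treatment effect.** A reader might infer that the report mistook noise between identical arms for an effect. The documents do not support that. The Results, Discussion and Conclusion claim no HP13–HP26 difference at week 4 or 13, and the Conclusion speaks of the two gel groups together. Testing HP13 against HP26 at both visits on PD, RAL and BOP would carry a 1 − 0.95⁶ = 26.5% chance of at least one false positive if the tests were independent, but no such tests are reported. Nor is chance shown to be the cause of the gap: baseline imbalance, attrition or adherence could contribute, and pooling would hide these rather than cure them.

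**Week 13 has no objective of its own.** This stands. Objective 1 covers six months, so a week-13 contrast can be supportive only.

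What survives is that objective 2 is a stated primary objective with no matching comparison in the plan or the report.

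**Conclusion.** The point holds as an unspecified contrast. The assigned regimens are identical through the week-13 measurements, objective 2 is a gel versus no-gel question at week 4, and no combined-gel estimate is planned or printed.

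At 20 per arm, naming the contrast is worth a quarter of the variance and about 12 power points over a pairwise test at 0.8 SD (11 at 0.6 SD). These rest on assumed effect sizes and on full recruitment and retention. At 3/3/9 the gain in SE is 3% or 21%, depending on the comparator, and power stays near 20% even at 0.8 SD.

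A reader might take the −13.6 BOP points as evidence that gel reduces inflammation before SRP. The documents do not support that: the figure moves to −8.1 under equal weights, rests on very few patients, and is accompanied by almost no combined difference in PD or RAL.

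The report's own statements also need reconciling. The Conclusion describes significant improvement in PD and attachment level in both gel groups after four weeks, while HP13 RAL rose from 6.97 to 7.29 mm and the Discussion finds no evidence of pocket reduction before SRP.

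**What to change.** - **Week 4 (objective 2):** specify a per-patient, baseline-adjusted comparison of HP13 and HP26 combined versus SRP, by pooling or as a contrast in the three-group ANCOVA. State the weights, since they matter when the arms are unequal.
- **Week 13:** report the same contrast as a supportive interim result for objective 1.
- **Week 26:** keep three separate groups.
- **HP13 versus HP26 at weeks 4 and 13:** show descriptively only, with numbers of patients per arm and visit, as a display of variation between arms with the same assigned treatment.
- **Schedule:** the SRP schedule lists no data collection at week 4, although week-4 SRP values are reported. Reconcile the two, because the contrast depends on those values.

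For a future protocol the cost is a few lines of analysis text, with no extra visits. Here it is a re-analysis of existing data. Because results by arm are already reported, it must be labelled post hoc and cannot be called confirmatory.

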## ABSTRACT OF THE THESIS

Custom Application of Peroxide Gel as Adjunct to Scaling/Root planning in Treatment of Periodontitis

by

[name]

Master of Science, Graduate Program in Periodontics

Loma Linda University, September 2019

[name] [name], Chairperson

**Aim:** This study was aimed to evaluate and compare the clinical effects of scaling and root planning (SRP) combined with local delivery of 1.7% HP in customized trays to that of SRP alone.

**Materials and Methods:** Sixty patients with generalized moderate to chronic severe periodontitis will be assigned to three groups treated by SRP plus HP gel with a custom prescription tray application. The test groups will receive twice daily 1.7% HP gel in custom trays four weeks prior to SRP and will continue to application for up to 3- and 6-months post-SRP. Baseline data that is collected at the start of the study will be collected again at 4, 13, and 26 weeks post-SRP and analyzed for any changes and thus main outcome variables will include changes in pocket depth (PD), relative recession (R-Rec), relative attachment level (RAL), and changes in bleeding (BOP) using ANCOVA of main effects.

**Results:** Repeated measure ANOVA showed significant difference in pocket depth among all time points in all treatment groups. Mean BOP was significantly reduced in all groups between 4-week examination and re-evaluation with mean BOP scores at final

examination staying similar to levels at re-evaluation for HP13 and HP26 groups. Mean BOP scores at final examination group for SRP group was similar to baseline.

**Discussion:** The use of adjunctive HP in custom fabricated trays presents with no adverse effects. Significant improvement was evident in pocket depth and attachment level in both treatment groups between after 4 weeks of using the tray. No significant effect found in SRP group between baseline and 4 weeks. After SRP, significant difference was seen in all three groups between 4 weeks and 3 months.

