There is no significant difference between the treatment groups with regards to attachment gain.

There is no significant difference between the treatment groups with regards to BOP.

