## CHAPTER FOUR

### DISCUSSION

This randomized, examiner-blind, parallel-design, clinical trial compared the effectiveness of SRP to daily treatment with 1.7% hydrogen peroxide using prescription, custom-fabricated dental trays as an adjunct to SRP. The results of this study demonstrate that the peroxide/prescription tray treatment regimen in combination with SRP is statistically significant in terms of reduction of BoP

In contrast to prior studies (Putt 2012, 2013 Journal of Clinical Dentistry), this study did not provide evidence to show that the use of peroxide/prescription tray regimen prior to SRP would reduce pocket depths without mechanical intervention. According to Putt 2012, the mean difference between test and control group after two weeks of 4-times daily use hydrogen peroxide was 0.44 mm in sites >5mm. The difference between test and control groups for all sites was 0.18mm. The difference that was seen between our study was that the subjects were instructed to use twice daily hydrogen peroxide, therefore the total “contact time” of peroxide is effective half.

The amount of marginal tissue recession over time did not demonstrate an increase of soft tissue recession over time with the use of the prescription trays indicated that the physical seal along the gingival margin does not induce or propagate recession.

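### Primary objective 2 (inflammation before SRP) has no named endpoint, time point or contrast, and no week 0 to 4 test of bleeding is reported

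*Combined protocol and SAP*

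**What the plan says.** Chapter One gives two primary objectives. The second is to "evaluate whether the custom tray delivery of the HP gel can decrease inflammation prior to SRP". The null hypotheses closing that chapter include one of "no significant difference between the treatment groups with regards to BOP", with no visit attached. No text links objective 2 to a variable, a visit or a comparison.

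The Statistical Analysis section of Chapter Two says three things about BOP:

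- It is primary: "The primary outcome variables are PD reduction, RAL gain, and reduction in BOP".
- It is also secondary: "Secondary efficacy variables were BOP, and MQH".
- Its method: "BOP was computed to provide a mean score per mouth for each clinical assessment and were analyzed using repeated measures (ANOVA").

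The only outcomes named in that section's between-arm comparison at every visit are PD and CAL: "between-treatment and within-treatment (longitudinal) comparisons of PD and CAL at all examination time points". The abstract differs on method: "main outcome variables will include changes in pocket depth (PD), relative recession (R-Rec), relative attachment level (RAL), and changes in bleeding (BOP) using ANCOVA".

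The Results print BOP by arm at each visit, including week 4. Their one significance statement on BOP covers week 4 to re-evaluation, which is after SRP. The Discussion says the study gave no evidence that the regimen "prior to SRP would reduce pocket depths without mechanical intervention". The Conclusion reports significant improvement in PD and attachment level in both gel groups after four weeks of tray use, and none in the SRP group.

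**The concern.** PD, recession and attachment level are distances, and the plaque index scores plaque. BOP is therefore the natural inflammation measure among those collected, although the documents never say so. A primary objective with no assigned outcome can be answered afterwards on whichever outcome the author picks up. Here the pre-SRP statements were made on PD and attachment level.

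Two things are at stake. First, PD and BOP need not agree over the four weeks before SRP, so the choice of outcome can change the apparent answer. Second, the reported answers do not agree even on PD: the Discussion finds no pre-SRP evidence and the Conclusion claims improvement. One might reconcile them by taking the first as between arms and the second as within arms, but the text does not say so. Significance in the gel arms and none under SRP would not in any case be a test between arms.

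**Working it through.** The plan gives no figure for objective 2 to reproduce. The check uses the means printed in the Results.

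**Inputs, baseline to week 4**

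| | SRP | HP13 | HP26 |
|---|---|---|---|
| Completers | 3 | 3 | 9 |
| PD, mm | 3.88 to 3.67 (-0.21) | 4.11 to 4.06 (-0.05) | 3.83 to 3.55 (-0.28) |
| RAL, mm | 7.16 to 7.02 (-0.14) | 6.97 to 7.29 (+0.32) | 7.04 to 6.69 (-0.35) |
| BOP, % | 45 to 45 (0) | 57 to 60 (+3) | 63.1 to 44 (-19.1) |

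The gel arms have the same regimen until week 13 (Treatment Phase), so they can be pooled for this period. Weighting by completers is an assumption: the documents do not say how many patients contribute to each week-4 mean.

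**PD.** Gel change = (3 × (-0.05) + 9 × (-0.28)) / 12 = -0.22 mm, against -0.21 mm with SRP: a difference of about -0.01 mm. With equal arm weights, -0.165 + 0.21 = +0.045 mm. Baseline adjustment hardly matters, because the pooled gel baseline is (3 × 4.11 + 9 × 3.83) / 12 = 3.90 mm against 3.88 mm.

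**RAL.** Gel change = (3 × 0.32 + 9 × (-0.35)) / 12 = -0.18 mm, against -0.14 mm: a difference of -0.04 mm. RAL is measured from the stent to the pocket base, so the HP13 rise is a loss. That conflicts with the Conclusion's claim of improved attachment in both gel groups.

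**BOP.**
- Gel baseline = (3 × 57 + 9 × 63.1) / 12 = 61.6%.
- Gel week 4 = (3 × 60 + 9 × 44) / 12 = 48.0%.
- Change = -13.6 points, against 0 with SRP.
- Equal weights: (3 - 19.1) / 2 = -8.05, about -8.1 points.

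**Dependence on baseline.** The baseline gap is 61.6 - 45 = 16.6 points. Adjusted difference = (48.0 - 45) - β × 16.6, where β is the slope of week-4 BOP on baseline BOP. The documents do not give β, so it is assumed:

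| β | Gel minus SRP, points |
|---|---|
| 0 (unadjusted) | +3.0 |
| 0.5 | -5.3 |
| 0.7 | -8.6 |
| 1.0 (change score) | -13.6 |

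**By initial depth.** The same weighting gives BOP differences in change of -18.5 points in sites under 5 mm (gel -13.5, SRP +5) and -2.0 points in sites of 5 mm or more (gel -3.0, SRP -1).

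**Precision.** The text gives no SD for BOP. For an assumed SD of 10 to 25 points and 12 against 3 patients, SE = SD × √(1/12 + 1/3) = 6.45 to 16.14. An approximate 95% half-width is 1.96 × SE = 12.6 to 31.6 points. Power for a true 13.6-point difference (two-sided 0.05, normal approximation) is 56, 29, 18 and 13% at SD 10, 15, 20 and 25.

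**The case against.** The strongest reply is that the plan does cover BOP. It is a listed primary outcome, scored at each assessment, with a between-group null and a repeated-measures analysis. The abstract puts it under ANCOVA, and the sentence on ANCOVA for follow-up data is not limited to PD and CAL. A week-4 comparison between arms is thus arguably within the plan. This stands: a reader might infer that BOP is excluded from between-arm testing, and the documents do not support that. They leave the comparison unspecified, and no such test is reported.

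A reader might also infer that objective 2 was decided on the wrong outcome and answered in the negative. That goes too far. No text maps the objective to any variable. The Discussion sentence is framed as a contrast with prior pocket-depth findings and does not claim to settle the objective. The Conclusion's answer on PD is positive.

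Finally, the BOP figures are fragile. The whole pooled fall comes from HP26, while HP13, on the same regimen at that stage, rose. Week-4 bleeding was still higher with gel (48.0%) than with SRP (45%). With 3 controls, an interval will settle little. All of this stands, and it is why the estimate needs its uncertainty shown.

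**Conclusion.** The point holds as a gap in specification with a visible consequence. A primary objective has no endpoint, visit or contrast. The bleeding measure has two roles and two methods. No test of it before SRP is reported, and the pre-SRP statements rest on other outcomes and conflict on PD.

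The outcome chosen changes the picture: about -0.01 mm for PD, against a BOP difference anywhere from +3.0 to -13.6 points over assumed slopes of 0 to 1. These figures rest on printed means and completer weights. A reader might take the -13.6 points as showing that the gel reduced bleeding. The documents do not support that, because the two gel arms move in opposite directions, the baseline gap is 16.6 points and there are 3 SRP completers. The effect has to be estimated from patient-level data.

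**What to change.** In Statistical Analysis:

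- Name per-mouth BOP at week 4, before SRP, as the outcome for objective 2, and give BOP one role throughout.
- Compare the pooled gel arms with SRP by patient-level ANCOVA on baseline BOP. Report the estimate with a 95% CI and show HP13 and HP26 separately. Align the abstract's and this section's method for BOP.
- Treat week-4 PD and RAL as supportive.
- Label the contrast as specified after results were seen, and note that the interval will be wide with 3 SRP completers.

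In Study Schedule, reconcile the SRP arm's week-4 entry, which lists no data collection, with the week-4 SRP values in the Results; the ANCOVA depends on those values. The gel arms' week-0 entry also omits BOP from its listed measurements.

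Restate the pre-SRP sentences in the Discussion and Conclusion around the between-arm BOP estimate, and remove their disagreement on PD.

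The cost is a few sentences and one model on data already reported, with no new visits. The price is that the result must be presented as post hoc and imprecise.
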